## **Study site**

The study will take place in Guangzhou MSM community service center. The center is supported by the Guangzhou CDC to provide HIV testing for MSM. Guangzhou MSM community center provides services for 8000 MSM each year, and all the newly identified MSM HIV positive cases in Guangzhou will be referred to the center for additional service. Given 12 months of enrolment, we have a strong ability to recruit 120 eligible MSM (Guangzhou city newly identified 950 MSM HIV cases in 2017).

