## **Eligibility**

Eligibility criteria include: (1) being born as a male, (2) 18 years old or elder, (3) at least one male or transsexual oral or anal sexual partner in the past six months, (4) newly identified as HIV positive, and (5) currently live in Guangzhou and no plan to leave Guangzhou in the following two months. To establish linkages for follow-up surveys, unique ID and access codes will be issued to each participant. Participants' phone number, email address, WeChat ID and Blued ID will be collected as tracking information for follow-up. Use of WeChat to contact participants will be particularly helpful given its broad uptake—846 million monthly active users as of November of 2016 and our previous experience in using WeChat to follow up over 80% of participants (1381 MSM). Unlike with phone numbers, people usually maintain a single WeChat account, even if they switch to a new phone number. Signed informed consent will be required from all participants.

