## **Index follow-up survey**

Three months after enrolment, index participants in both arms will be re-contacted by phone or email and provided a link to an online survey. A small incentive (mobile top-up) will be provided. The survey will further evaluate the acceptability and feasibility of the crowdsourced intervention among participants in the intervention group. We will also evaluate the potential challenges and advantages of the crowdsourced intervention. The survey will be comparable to the baseline survey. Sexual contact with specific partners, named previously, will be elicited, as well as new partners. The survey will also address whether the specific partners were notified by the index, underwent HIV testing, and how testing was performed.

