## **Study measures and outcomes**

### **Primary outcomes**

The primary outcomes are: 1), the feasibility of the study and the feasibility of the intervention. The feasibility of the study will be measured in the ability to enroll 120 newly identified MSM HIV cases as index participants in the study center in a 12-month period, and the ability to

contact the index MSM (follow-up rate) and their partners at 3 months after enrolment (proportion of the surveyed partners response to the survey). The feasibility of the intervention will be used to measure whether the crowdsourced intervention is successfully used or carried out. This will be measured in the frequency of the partners in the intervention arm receiving the crowdsourced intervention and the frequency of the partners taking action after they receive the intervention (whether go for HIV testing). 2), the acceptability of the crowdsourced intervention: this will be measured at baseline among index participants and the partners of the index participants in the intervention arm. We will ask the index participants and their partners whether the crowdsourced intervention is acceptable to them. 3), the preliminary impact of the intervention: the proportion of partners returning for HIV testing within 3 months of the index participant's enrolment in the study, determined based on the partners presenting to the centers and those verified from the CDC electronic medical record central database.

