## **Secondary outcomes**

Secondary outcomes will include: 1) The proportion of partners being notified by indexes among all reported partners; 2) the number of tested partners, normalized to the number of index participants (i.e. the mean number of partners getting notified per index participant); 3) the proportion of positive HIV tests among tested partners; 4) the number of tested partners with a positive HIV test, normalized to the number of index participants (i.e. the mean number of partners with HIV per index participant); 5) the proportion of reported partners getting HIV testing who are not spouses or regular partners, and 6) the proportion of condom use by presenting partners during the last anal intercourse.

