## Statistical Analysis Plan

For the primary outcomes of feasibility and acceptability of the intervention: this will be analyzed through descriptive analysis to assess the feedback on the feasibility and acceptability of the crowdsourced PS intervention among index MSM and their partners in the intervention group. For the primary outcome of the proportion of partners returning for HIV testing within 3 months of the index participant's enrolment in the study, log-binomial regression (generalized linear model with binomial distribution and log link) will be used to calculate 95% confidence intervals for the proportion of notifiable partners visiting by arm. Risk differences and risk ratios will also be calculated in these models. As this study is a pilot RCT, and we will only recruit 120 index MSM, and they will be randomly assigned in a 2:1 ratio, adjustment for covariates would be necessary if the two study arms are not balanced. In secondary analyses, we will adjust for pre-specified potential confounding variables that might bias the estimate if not accounted for (e.g. index age, index marital status). If a partner reports more than one index referred him, he will be counted as a returning partner for each identified index.

*Table 1* Analysis strategies for secondary outcomes

Secondary Outcome	Population	Model Type
The proportion of reported partners being notified by indexes among all reported partners	Reported sexual partners	Binomial regression, robust variance
Mean number of partners tested per index participant	Index participants	Poisson or negative binomial regression, robust variance
The proportion of positive HIV tests among tested partners	Tested sexual partners	Binomial regression, robust variance
Mean number of partners with HIV (case-finding) per index participant	Index participants	Poisson or negative binomial regression, robust variance
The proportion of reported partners getting HIV testing who are not spouses or regular partners	Reported casual male sexual partners	Binomial regression, robust variance
The proportion of presenting partners reporting condom use during the last anal intercourse	Presenting sexual partners	Binomial regression, robust variance

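### Partners notified before randomisation count as notification successes in both arms, and the testing denominator has no clear rule for partners already tested

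*Combined protocol and SAP*

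**What the plan says.** - **Entry.** The Eligibility section asks that the index man be "newly identified as HIV positive" and sets no maximum time since diagnosis. The Study site section adds that "all the newly identified MSM HIV positive cases in Guangzhou will be referred to the center for additional service". Diagnosis can therefore precede enrolment by an unstated interval.
- **Partners.** The Baseline questionnaire section covers partners of the previous six months. The partner-level items it lists are sexual behaviours and contact details. It does not mention whether each partner has already been told or tested.
- **Notification outcome.** Secondary outcomes defines it as "The proportion of partners being notified by indexes among all reported partners", and Table 1 of the Statistical Analysis Plan analyses it among reported sexual partners. The Index follow-up survey at three months asks "whether the specific partners were notified by the index, underwent HIV testing, and how testing was performed". No date, and no split at enrolment, is stated.
- **Testing outcome.** Primary outcomes counts "the proportion of partners returning for HIV testing within 3 months of the index" man's enrolment, "determined based on the partners presenting to the centers and those verified from the CDC electronic medical record central database". The Statistical Analysis Plan describes the analysed quantity as "the proportion of notifiable partners visiting by arm" and does not define *notifiable*. It reports risk differences and risk ratios.
- **Use of the results.** Sample size and power says the trial is not powered to compare the arms and is meant to supply data for sizing a full RCT. The end of the Statistical Analysis Plan repeats this and adds that secondary outcomes will be chosen for the full trial by how well they discriminate.

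**The concern.** Partner services are triggered by the diagnosis, but the trial's clock starts at enrolment. The Background and Study design overview describe card-based passive referral as the existing routine in China, so some index men may have told partners before allocation. A partner told before allocation cannot have been notified because of the assigned arm, yet nothing in the notification outcome removes him, and he scores as a success whichever arm the index enters.

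The testing outcome has a related but weaker problem. A test after the index's diagnosis but before enrolment falls outside the window. If that partner is not retested, he may stay in the denominator as a non-event.

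At stake are the absolute rates and effect sizes carried into the full trial's sample size, and the judgement on whether notification discriminates well enough to be kept as an outcome.

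**Working it through.** **Inputs.** From Sample size and power: 40 control and 80 intervention, control partner return rate 30%, alpha 0.05, power 0.80, minimal detectable difference 26.7 points. The comparison rate is 30% + 26.7 = 56.7%. The documents give no share of partners reached before enrolment, so 10% and 20% are assumed. They also give no notification rates for this trial, so the testing rates are borrowed for illustration.

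**The plan's own figure.** A two-sided pooled comparison of two proportions, treating the 40 and 80 as independent units:
- Pooled proportion = (40 × 0.30 + 80 × 0.567) / 120 = 0.478.
- Null standard error = √[0.478 × 0.522 × (1/40 + 1/80)] = 0.0967.
- Alternative standard error = √[0.30 × 0.70/40 + 0.567 × 0.433/80] = 0.0912.
- z = (0.267 − 1.96 × 0.0967) / 0.0912 = 0.85, so power is 80.2%.

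Solving for exactly 80% gives 26.6 points, so the stated 26.7 is reproduced.

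**Notification.** Let p be the share already notified before randomisation, equal in the two arms on average. Each such partner is a success, so the observed rate is p + (1 − p) × rate.

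| p | Control | Intervention | Risk difference | Risk ratio |
|---|---|---|---|---|
| 0 | 30.0% | 56.7% | 26.7 | 1.89 |
| 10% | 0.10 + 0.90 × 0.30 = 37.0% | 0.10 + 0.90 × 0.567 = 61.0% | 24.0 | 1.65 |
| 20% | 0.20 + 0.80 × 0.30 = 44.0% | 0.20 + 0.80 × 0.567 = 65.4% | 21.4 | 1.49 |

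Both effect measures shrink.

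**Testing.** Here p is a different share: partners tested after the index's diagnosis but before enrolment, not retested in the window, and kept in the denominator. Each is a non-event, so the observed rate is (1 − p) × rate.

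| p | Control | Intervention | Risk difference | Risk ratio |
|---|---|---|---|---|
| 0 | 30.0% | 56.7% | 26.7 | 1.89 |
| 10% | 0.90 × 0.30 = 27.0% | 0.90 × 0.567 = 51.0% | 24.0 | 1.89 |
| 20% | 0.80 × 0.30 = 24.0% | 0.80 × 0.567 = 45.4% | 21.4 | 1.89 |

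The factor (1 − p) cancels in the ratio, so only the absolute rates and the risk difference move. If p is instead the share tested early, the falls in the risk difference are upper limits, because some of these partners may retest and the SAP's denominator may already leave them out.

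**Does excluding them cost more than it gains?** On the same 40/80 basis, exclusion restores 30% v 56.7% but cuts the denominators to 36/72 or 32/64. Power at p = 10% and 20% is then 76% and 71%. Keeping them gives 72% and 63% when they count as failures, and 71% and 61% when they count as successes.

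**The case against.** Several parts of the opposing case stand.

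- **The testing denominator may already be right.** The SAP's *notifiable partners* could have been meant to leave out men already reached. A reader might infer that the plan states their inclusion as failures. It does not: the term is undefined, and that is the defect.
- **Not every contrast is diluted.** A reader might infer that the testing risk ratio shrinks too. The tables show that it stays at 1.89.
- **Notified is not tested.** It is tempting to say that every partner already reached is a testing failure who cannot respond. A partner told but not yet tested can still receive the materials, test within the window and count as a success. A tested partner can retest.
- **The size is assumed.** Adding p to the post-enrolment yield puts total control testing at 10 + 27 = 37% or 20 + 24 = 44%. Sample size and power gives about 31% for Guangzhou in 2016, without saying when its clock starts, and the Background cites 21.8% notified and tested in another Chinese study. A 20% share tested before enrolment therefore looks high.
- **Prior exposure is inferred.** Referral to the centre does not show that partner services were delivered elsewhere first, and the centre itself provides testing. The questionnaire is not in the documents, so its summary's silence on prior notification is weak evidence.
- **The planning input may be valid.** If the full trial keeps the same definitions and a similar delay from diagnosis to enrolment, the observed rates are the right ones for sizing it.

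One part does not stand: that data already planned would repair the gap. Additional measures collects testing and partner-services history from index men and *presenting* partners only, so a partner who tested early and never presents is missed. The Partner linkage text takes dates only from partners who cannot produce the card or message. Neither is used to define a denominator.

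**Conclusion.** The concern holds for notification and in a limited form for testing. As written, a notification made between the index's diagnosis and randomisation counts as a success in either arm, which shrinks both the risk difference and the risk ratio (1.89 to 1.65 or 1.49 in the illustration). For testing, the denominator is undefined. If it keeps partners tested before enrolment and not retested, the absolute rates and the risk difference fall, at most from 26.7 to 24.0 or 21.4 points, with no change in the risk ratio.

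These sizes rest on assumed shares of 10% and 20%, equal shares in the two arms, and testing rates borrowed for notification. A reader might infer that one arm is favoured. The documents do not support that: these partners are reached before allocation, so randomisation balances them on average. Because the trial disclaims power for the arm comparison, the harm falls mainly on the estimates used to size the full trial and choose its outcomes. This is a cheap improvement worth making, not a flaw that invalidates the pilot.

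**What to change.** 1. In the partner-by-partner part of the baseline questionnaire, completed before randomisation, record whether each partner has been notified, and whether he or she has been tested, since the index's diagnosis. Record the diagnosis date.
2. In the three-month index survey, ask the date of each notification.
3. Analyse notification among partners not yet notified at baseline, counting only notifications after randomisation.
4. In the Statistical Analysis Plan, define a notifiable partner, for the testing proportion, as a reported partner not already tested since the index's diagnosis. Keep partners who were notified but not tested, because they can still respond. Apply the same rule to the number of partners tested per index.
5. Report the versions based on all reported partners as sensitivity analyses.

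The cost is a short status item per partner in an existing survey, one diagnosis date, one dated follow-up question and some SAP wording. The denominators become somewhat smaller, and the analysis relies on the index's own report of earlier notification and testing. That report is given before allocation, so its errors cannot depend on arm; recall collected only at three months could.

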## **Secondary outcomes**

Secondary outcomes will include: 1) The proportion of partners being notified by indexes among all reported partners; 2) the number of tested partners, normalized to the number of index participants (i.e. the mean number of partners getting notified per index participant); 3) the proportion of positive HIV tests among tested partners; 4) the number of tested partners with a positive HIV test, normalized to the number of index participants (i.e. the mean number of partners with HIV per index participant); 5) the proportion of reported partners getting HIV testing who are not spouses or regular partners, and 6) the proportion of condom use by presenting partners during the last anal intercourse.

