## Methods and study design

### Study design overview

This study will use a pilot RCT comparing the crowdsourced PS intervention to standard PS. In China, a passive referral is the only existing PS model for HIV PS. We will conduct a pilot study to refine the components and procedures of the intervention and test the feasibility and acceptability of the crowdsourced PS intervention. Newly identified MSM HIV cases will be recruited from Guangzhou. After completion of a baseline survey, eligible MSM will be randomized individually to either the crowdsourced intervention or conventional PS (control arm) in a 2:1 ratio. In both arms, partners will be instructed to report to the study site sites for HIV testing and will complete a brief sexual history questionnaire upon presentation. We will re-contact them within three months of enrolment to confirm whether the intervention or control PS procedures were implemented by the index. The primary outcome will be 1) the feasibility and acceptability of the intervention; 2) the preliminary impact of the intervention: by comparing the proportion of partners getting HIV testing between the intervention and control groups. Secondary outcomes will be the number of partners getting notified, the number of testing partners with confirmed HIV, and risk behaviors of partners. We will also observe these secondary outcomes among main male partners and casual partners separately. We hypothesize that: 1) a crowdsourced PS approach is feasible and acceptable, 2) as compared to conventional PS, will yield: a) more sexual partners reporting for HIV testing; b) more sexual partners getting notified; c) more sexual partners with confirmed HIV; and d) a set of sexual partners with greater STI risk behaviors, such as more receptive anal intercourse, and less condom use.

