## **Baseline questionnaire**

After enrolment, participants will complete a brief self-administered baseline questionnaire. Study staff will be available to assist in the event of confusion about specific questions or if participants do not have a sufficient reading level to complete the survey on a tablet. The questionnaire will address socio-demographic characteristics and HIV testing history. A more detailed, partner-centric sexual history will be obtained by focusing on sexual partners in the previous six months. The sexual history will include specific behaviors with individual partners, including receptive/insertive anal sex, performing/receiving oral sex, condom use, and frequency of each type of intercourse. Information on sexual orientation and sexual orientation disclosure status will also be collected. Detailed contact information will be obtained for the participants and sexual partners for the past six months. Contact information will include phone number, email address, WeChat ID, QQ ID, and smartphone-based sex-seeking applications ID (i.e., Blued ID).

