Subgroup analyses will be performed by partner type (e.g. main male partner vs. casual male partner). For secondary outcomes, analysis approaches are provided in Table 1. For count variables expressed as the mean number of partners, we will use either Poisson regression or negative binomial regression if overdispersion is identified. In addition, we will assess which secondary outcomes seem to have meaningful discriminatory power in a future study. We will include the potential secondary outcomes that are important and meaningful discriminatory

power in the future study. In addition, we will use the information we obtain in the pilot RCT to conduct sample size estimation for the later trial.

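### The tested-partner count model leaves out the baseline partner count, a free pre-randomisation covariate that can add precision; two wording slips should be corrected with it

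*Combined protocol and SAP*

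**What the plan says.** **Count models.** Table 1 of the Statistical Analysis Plan lists "Mean number of partners tested per index participant", analysed over index participants by Poisson or negative binomial regression with robust variance. The number of HIV-positive partners per index gets the same model. The text after the table adds only the choice between the two: "For count variables expressed as the mean number of partners, we will use either Poisson regression or negative binomial regression if overdispersion is identified". Neither place names a covariate. The SAP's adjustment sentences stand in the paragraph on the primary outcome. They tie adjustment to imbalance between the arms and to confounding, and give index age and marital status as examples.

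**What is known before allocation.** Study design overview: "After completion of a baseline survey, eligible MSM will be randomized individually". Baseline questionnaire: "A more detailed, partner-centric sexual history will be obtained by focusing on sexual partners in the previous six months". The Randomization section accepts that the number of partners differs between indexes. It then expects similar partner totals in the two arms, although the sample size section plans 80 and 40 indexes.

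**Outcome definition.** Item 2 under Secondary outcomes is "the number of tested partners, normalized to the number of index participants (i.e. the mean number of partners getting notified per index participant". The Study design overview says "Secondary outcomes will be the number of partners getting notified, the number of testing partners with confirmed HIV" and hypothesises "b) more sexual partners getting notified". The only notification row in Table 1 is "The proportion of reported partners being notified by indexes among all reported partners".

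**The concern.** An index with one listed partner can send at most one of them for testing; an index with eight can send eight. Part of the spread in tested partners per index is therefore spread in partner numbers, which has nothing to do with the arm. With only 40 control indexes, a chance difference in mean partner number moves the rate ratio directly. A covariate fixed before randomisation can remove that part of the noise.

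The stake is modest but real. These are secondary outcomes of a declared pilot, but the SAP will use them to judge which outcomes could separate the arms in a full trial, and will use the pilot to size that trial. Avoidable noise feeds into both decisions. If the covariate is chosen only after the data are seen, the choice is open to selection.

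The wording matters less. Item 2 names two different steps, testing and notification, as one quantity. The sentence on totals does not fit the 2:1 allocation.

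**Working it through.** **1. The plan's own figure.** The documents give no precision figure for the counts. The one figure they give, a detectable difference of 26.7 points in the primary proportion, reproduces. With 30% against 56.7% and n = 40 and 80, the pooled proportion is (40 × 0.30 + 80 × 0.567)/120 = 0.478.

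- Null SE = √[0.478 × 0.522 × (1/40 + 1/80)] = 0.0967
- Alternative SE = √(0.21/40 + 0.567 × 0.433/80) = 0.0912
- Power = Φ[(0.267 − 1.96 × 0.0967)/0.0912] = Φ(0.85) = 0.80

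Nothing below changes that figure.

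**2. Partner totals.** With a mean of m partners per index, the expected totals are 80m and 40m. For m = 3 that is 240 and 120, a ratio of 2:1. Only the mean per index is expected to be equal.

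**3. How much the count can explain, by hand.** Let an index have m partners, one main (testing probability a) and m − 1 casual (probability c). Then

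- E(T | m) = a + c(m − 1), so the part of the variance due to partner number is c² × Var(m);
- the rest, without clustering, is a(1 − a) + c(1 − c)(mean − 1).

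The share due to partner number is roughly the most by which the covariate can cut the variance of the log rate ratio. Assumed here: mean 3, SD 2.8, so Var(m) = 7.84. Two casual rates are set so that overall testing equals a figure in the documents: c = (mean × overall − a)/(mean − 1), with a = 50%.

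- Overall 21.8% (Background, two Chinese cities): (3 × 0.218 − 0.5)/2 = 7.7%
- Overall 30% (sample size section): (3 × 0.30 − 0.5)/2 = 20%

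| Testing pattern | Due to partner number | Rest | Share | Simulated cut, ICC 0.1 |
|---|---|---|---|---|
| All partners 30% | 0.09 × 7.84 = 0.706 | 0.21 × 3 = 0.630 | 53% | 39% |
| Main 50%, casual 20% | 0.04 × 7.84 = 0.314 | 0.25 + 0.16 × 2 = 0.570 | 35% | 26% (SD 0.226 to 0.194) |
| Main 50%, casual 7.7% | 0.0059 × 7.84 = 0.046 | 0.25 + 0.071 × 2 = 0.392 | 11% | 7% (SD 0.224 to 0.216) |

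The simulated cuts are lower because partners of one index are correlated and 5% of counts were made missing or zero. The SDs are those of the log rate ratio; for example 1 − (0.194/0.226)² = 26%.

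**4. Simulation over a wider range.** Null trials of 80 against 40 indexes; partners = 1 + negative binomial, mean 2 to 4 in total; ICC 0.1 and 0.3; Poisson model with and without the log count.

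- Overall testing 21.8%: cut of −1 to 22%, equivalent to 119-154 indexes in place of 120, by 120/(1 − cut).
- Overall testing 30%: cut of 4.5 to 42%.
- Main 50% with casual 15%, 10% or 5%: 5-20%, 3-12% and 0-5%.
- Every partner at 30%: 18-44%. A second set of runs reached about 50% at most.
- HIV-positive partners (assumed 20% positivity): 0% and 3% in the mean-3 example at casual 7.7% and 20%; −1 to 15% over the whole range; 0-3% in the second set.
- Type I error, tested partners: 4.3-7.9% unadjusted, 4.2-7.7% adjusted.
- Median null rate ratio: 1.00-1.03 unadjusted, 0.99-1.02 adjusted.

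Values within about 1% of zero are simulation noise. These runs used log(count + 1). Repeating the mean-3 example with log(count) and zeros treated as missing moved the cut by less than two points.

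**5. Tested or notified.** Item 2 says tested and then explains it as notified. Table 1 has tested for the per-index count and notified only as a proportion. The overview lists a number notified. Table 1 therefore settles item 2 as tested, and the notified count in the overview has no count analysis.

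**The case against.** The strongest reply is that nothing here is wrong. An unadjusted randomised comparison of mean tested partners per index is valid and matches the stated outcome. The list of adjustment variables is open-ended and does not exclude partner count. The pilot disclaims power, and because the partner list is collected, the investigators could work out adjusted variances when they plan the full trial. The gain rests on assumed distributions and may be nil. The Background figure that only 16.2% of HIV-infected MSM had notified casual partners points to the lower scenarios.

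Most of that stands, and it limits this to an improvement at no cost. It does not remove the point: the open list is not tied to the count models, and a covariate picked later is not pre-specified.

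A reader might infer more, and the documents do not support it:

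- *That the unadjusted ratio is biased.* Randomisation protects it, and the null medians show no bias.
- *That the gain is large.* If every partner within an arm has the same testing probability (30% against 45%), with no clustering and means of 2 to 5, the cut is 17-67%, and power at mean 3 can rise from 0.48 to 0.77. Nothing in the documents supports equal testing by main and casual partners.
- *That item 2 has no usable definition, or that the notification hypothesis goes untested.* Table 1 gives the first, and its proportion notified can address the second.
- *That the sentence on totals damages an analysis.* No listed analysis uses totals.

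**Conclusion.** The point holds as a precision improvement for one secondary outcome of a pilot, with two wording corrections. For tested partners the variance cut lies between about 0% and about 40-50%. Where it falls depends mainly on how often casual partners test, which the documents do not say; the partner mean, spread and clustering are also assumed. If overall testing is near 21.8%, expect the lower half of that range or nothing. For HIV-positive partners the gain is near zero, so the case for changing that model is consistency only. Type I error is about the same with and without the covariate.

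**What to change.** **Count model.** In Table 1, pre-specify log(number of partners reported at baseline) as a covariate in the tested-partner model, regardless of observed balance, and report the unadjusted ratio alongside. Enter it as a covariate, not an offset: an offset forces tested partners to rise in proportion to listed partners, which fails if main and casual partners test at different rates. Use the baseline list only, since partners first named at three months come after allocation. The same covariate in the HIV-positive model is optional.

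**Zero and missing counts.** Eligibility requires at least one male or transsexual partner in the same six months. Treat a reported zero as a data query and, if it is not resolved, as missing. Set missing counts to the median of all indexes, computed without regard to arm.

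**Outcome wording.** Make the explanation in item 2 say tested, and reconcile it with the number notified in the Study design overview. If a notified count is kept, give it its own row in Table 1. Word the three-month survey item identically in both arms to cover notification by any route. As described, it asks about notification by the index, while in the intervention arm the coordinator, the CBO or an anonymous system may send the message, so notifications could be missed in that arm alone.

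**Randomization section.** State that expected partner totals are 2:1 and that the mean number per index is expected to be comparable.

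**Cost.** A few sentences and at most one table row. The partner count is derived from a list already collected. Only the survey item, if the notified count is kept, changes a data form.
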